4.1. Preface

Immunoglobulins are a derivate of plasma proteins used as therapeutic treatment for patients with antibody-deficiencies and for a wide range of diseases, such as immunomodulatory or replacement therapies (Ruiz-Antorán, 2010)(Vallejo Rodríguez, 1999). Its use has increased over the last few years, especially since the COVID-19 outbreak (AminJafari, 2020). They have been used to try to combat respiratory infection by SARS-CoV-2. However, only some indications have been authorized by the Spanish Medicines Agency (AEMPS) based on contributed evidence. Immunoglobulins are not only used for these indications but are also used for several conditions not included in the regulatory approvals but for which substantial clinical evidence exists (Farrugia, 2001). Moreover, there has been a significant increase in the price per unit of immunoglobulins, due to the increased complexity of manufacturing processes, including safety enhancements and stringent regulatory requirements (N'kaoua, 2021). The use of immunoglobulins for non-approved indications without evidence, the increase in consumption and its high costs have already promoted the rationalization of its use through a

consensus in other countries. Different consensus and guidelines have attempted to establish priorities and to optimize the use of immunoglobulins (Ruiz-Antorán, 2010).

In 2014 a register was implemented in Catalonia to carry out the task of monitoring data on the use of high-cost drugs in normal clinical practice conditions: the Registry of Patients and Treatments (RPT). Its objective is to measure the quality criteria of the care process and health outcomes through the systematic collection of data on the effectiveness and safety of drugs under normal clinical practice conditions. From September 2019 on it is obligated to report immunoglobulins in the RPT (Roig Izquierdo, 2020).

4.2 Purpose of the specific analyses

Immunoglobulins represent a therapeutic option with high economic costs and limited availability. Therefore, by describing the use of immunoglobulins through RPT, evaluating the indications for which they are being used and by comparing the usage with clinical recommendation guidelines, risks can be limited and the best possible clinical results can be obtained. The protocol of this study and the approval form (CEIm) are attached in annex 1 and 2.

5. Study objectives

objective 1: to describe the use of immunoglobulins in the HUVH, HUB and HGTiP.

objective 2: to validate the indications for use of the non-specific immunoglobulins in the RPT of the HUVH, HUB and HGTiP.

6. Study Methods

6.1. General study design

We will perform an observational, retrospective, multi-centered study in a cohort of users of non-specific immunoglobulins. Naive incident users in the RPT registry will be included.

6.1.1. Base population

The inclusion criteria are: all the naive incident users who initiate a treatment with non-specific immunoglobulins (J06BA01 and J06BA02) in the period between September 2019 and December 2021 regardless of their age, sex, indication, dose and duration. And without immunoglobulins use in the year before the treatment initiation date.

A preliminary count of registered treatments indicates that around 500 patients would meet these inclusion criteria.

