6.2.1. Exposures

All the patients included in the study are exposed to non-specific immunoglobulines, this could be an extra- (J06BA02) or intravascular (J06BA01) administration.

List of definitions:

Naive incident user: a patient who isn't exposed to immunoglobulines (intra- or extravascular) a year prior to the start of the treatment with a non-specific immunoglobulin.

Immunoglobulin switching: the patients who changed immunoglobulin therapy from extravascular to an intravascular administration or vice versa during the study period providing that the period in between therapies is less than a year, regardless of the indication. In cases where two immunoglobulin types overlap in time, we won't consider them as switchers.

Immunoglobulin concomitance: if an overlapping use of an intravascular and an extravascular immunoglobulin of at least one day, regardless of indication. If cases are found they will be narratively described.

Immunoglobulin discontinuation: the patients who stopped the use of any type of non-specific immunoglobulines (J06BA01 and J06BA02) for a year or longer.

Duration of treatment: When there is a certain period between the start date and end date of the use of immunoglobulin.

Patients with multiple indications: In RPT each treatment initiation is linked to a single indication. When a patient meets multiple treatment initiations, different diagnosis for each may be found. In this case, if the patient does not meet any of the previous definitions (switching or discontinuation) and is treated with the same type of IGG administration (extra- or intravascular), they will be reviewed case by case. From this review, it will be decided based on medical criteria whether diagnoses are a specification of the other (e.g., transplant versus transplant rejection), or if they are clearly referring to different clinical entities. For both situations, if cases are found they will be narratively described.

These group of patients will not be taken into account during the validation of the RPT (see 6.3).

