8.2. Strengths and limitations because of datasource

The strength of the RPT is that the register is implemented in Catalonia by health professionals from the Comprehensive Public Health System of Catalonia (SIS CAT) to carry out the task of monitoring the data on the use of high-cost drugs in normal clinical practice conditions. It consists of three levels of information: treatment level, initiation level and follow-up level. Just the availability of the RPT represents opportunities for analysis and the generation of support information for management decision-making.

There are also some limitations regarding the data source. The database that is used is specific for Catalonia and only Catsalut hospitals participate, which means that the generalizability is limited. In addition, it has only been mandatory since 2019 to register immunoglobulins in the RPT, for that reason the data source is relatively new and possibly less reliable. This also means that no information was available before 2019 about the use of immunoglobulins in the RPT, which again could lead to decreased reliability of the results. A possible other limitation is that different clinicians provide the RPT with information, the consistency of the database could therefore be questioned. Moreover, there is limited information available about the costs as they may vary across different brands (which are not present in the RPT registry), thus the yearly mean costs are used. Thereby, it is assumed that the administrations are given monthly based on the data extraction (dose/month). The reliability of this information could be questioned: some immunoglobulins require weekly/biweekly administrations.

9. Results spreading plan

The knowledge and results obtained because of this study will be disseminated through conferences, internal talks, journals and as training material.

References

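### The one-year immunoglobulin-free look-back that defines a naive user cannot be fully verified in the RPT for starts from September 2019 to August 2020

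*SAP*

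**What the plan says.** Four statements in the SAP bear on this point.

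- **Who is eligible.** Section 6.1.1 takes patients who start "in the period between September 2019 and December 2021 regardless of their age, sex, indication, dose and duration", with the added condition "And without immunoglobulins use in the year before the treatment initiation date". Section 6.2.1 defines the naive incident user in the same terms: "a patient who isn't exposed to immunoglobulines (intra- or extravascular) a year prior to the start of the treatment".
- **Where naive status is read.** Section 6.1: "Naive incident users in the RPT registry will be included". The SAP text names no other source for prior exposure. Section 6.3 uses the hospital record as gold standard for the diagnosis only.
- **When the registry began to capture the drug.** Section 4.1: "From September 2019 on it is obligated to report immunoglobulins in the RPT". Section 8.2 says "it has only been mandatory since 2019 to register immunoglobulins in the RPT" and that "no information was available before 2019 about the use of immunoglobulins in the RPT".
- **What is claimed for the cohort.** Section 8.1 states that naive incident users alone are in the study and prevalent users are not. Section 8.2 treats the missing history as a matter of possibly lower reliability. It does not connect it to the look-back or plan any check.

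**The concern.** Entry opens in the month in which reporting became compulsory. For a patient who starts early in the window, most of the year that must be free of immunoglobulins lies before that date. If earlier treatment was never entered in the RPT, its absence reads as non-use and the patient passes the criterion.

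Objective 1 describes new users. Section 6.2.4 reports median age, follow-up and treatment duration, and section 6.2.2 the share of patients by indication and evidence group. If a continuing user is counted as new with a later start date, age at start is too high and duration too short. Continuing users are also more likely to have long-term indications, so the shares would move towards those.

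No planned step would reveal this. The validation form in section 6.3.2 has no prior-use item. The quality checks in section 6.6 look at missingness, counts and date consistency, and cannot find treatment that was never recorded.

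**Working it through.** **Inputs.** Entry window September 2019 to December 2021, look-back one year, about 500 patients (section 6.1.1). Mandatory reporting from September 2019 (section 4.1). No RPT immunoglobulin data before 2019 (section 8.2). Validation samples of 173 from 500 records and 122 from 224, with expected proportion 78%, precision ±5% and 95% confidence (section 6.3.1).

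**The plan's own figures.** n0 = 1.96² × 0.78 × 0.22 / 0.05² = 263.7. With the finite population correction n0 / (1 + n0/N):

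- N = 500: 172.6, rounded up to 173.
- N = 224: 121.1, rounded up to 122.

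Both reproduce and are not in dispute. They matter here only because they depend on the cohort size.

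**Length of the window.** 4 + 12 + 12 = 28 months.

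**Reading A: capture begins with mandatory reporting, September 2019.** The first start with 12 months of mandatory history is 1 September 2020. Starts from September 2019 to August 2020 fall short: 12/28 = 42.9%. Within that year the observed look-back grows from 0–1 month (September 2019) to 11–12 months (August 2020). The mid-month average is (0.5 + 1.5 + … + 11.5)/12 = 6 of the required 12 months.

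**Reading B: some voluntary records exist from January 2019.** Section 8.2 says before 2019, not before September 2019. On this most favourable reading, part of the look-back is wholly absent only for starts from September to December 2019: 4/28 = 14.3%. Starts from January to August 2020 have some capture throughout, but part of it rests on non-mandatory reporting of unknown completeness.

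**Patients.** The SAP gives no monthly counts, so the share of starts in the first 12 months is an assumption.

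| Share of starts in first 12 months | Without full mandatory look-back | Starts from September 2020 | Validation sample at same precision |
|---|---|---|---|
| 30% | 150 | 350 | 151 |
| 42.9% (even accrual) | 214 | 286 | 138 |
| 50% | 250 | 250 | 129 |

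Under even accrual, HUVH has 224 × 12/28 = 96 such patients. Under reading B, starts from September to December 2019 number 500 × 4/28, about 71.

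**The case against.** The strongest reply is that incomplete look-back is not misclassification. Section 6.1.1 ties eligibility to the date treatment began, and section 6.1.2 describes a separate initiation level in the registry. If an established user was registered with the true earlier start date, that date lies before September 2019 and the entry window excludes the patient. Nothing in the SAP says that existing users were registered in bulk or given later start dates. The annexes, including the variable extraction table, are not shown and could name another source. This stands as a limit on the consequence. It does not restore verification, because the SAP text neither states that registered start dates are the true ones nor describes a check.

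Three stronger readings are tempting and should not be drawn:

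- *That the look-back is unobservable up to August 2020.* It is partly observed, and increasingly so, across that year.
- *That about 214 prevalent users enter the cohort.* That figure counts patients with incomplete look-back under an accrual assumption. The number of continuing users among them is unknown.
- *That cost per month is distorted through the start date.* The formula in section 6.2.3 uses weight, dose and price, and neither start date nor naive status enters it.

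It is also fair that accrual could be later than even, since section 4.1 reports rising use since the COVID-19 outbreak; the range above allows for this. The positive predictive value in objective 2 does not depend on naive status. Section 8.2 does disclose the missing history, but that disclosure does not support the flat statement in section 8.1.

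**Conclusion.** The concern holds as a defect of verification. On the SAP's own dates, naive status cannot be fully confirmed in the RPT for starts in 12 of 28 entry months: about 214 of 500 patients under even accrual, or 150 to 250 if 30% to 50% of starts fell in those months. On the reading most favourable to the plan, a wholly missing stretch is certain only for 4 of 28 months, with a further 8 resting partly on voluntary reporting.

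Continuing users may therefore be counted as new. Bias in age at start, treatment duration and indication shares follows only if their earlier use went unrecorded and a later start date was entered, which the SAP neither establishes nor rules out. The exclusion of prevalent users in section 8.1 is stated with more certainty than the data source allows.

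**What to change.** 1. Keep the full cohort as the main description, label it *first RPT registration*, and state that naive status is unverified for starts before September 2020.
2. Pre-specify the objective 1 results for starts from September 2020 beside it as a sensitivity analysis. Note the smaller number (about 286 under even accrual) and the shorter follow-up. If follow-up ends in December 2021 (an assumption), these patients have at most 16 months, which leaves little room for the discontinuation definition in section 6.2.1, a year or longer off treatment. For this reason the restricted cohort is better as a sensitivity analysis than as the primary one.
3. Add to the validation form (section 6.3.2) any immunoglobulin use in the year before the start and the date of first immunoglobulin. Of 173 sampled patients, about 173 × 12/28 = 74 would be first-year starts under even accrual. The false-naive share among them could then be estimated to within about 1.96 × √(0.25/74) = ±11 percentage points at worst, before finite population correction.
4. Correct the statement in section 8.1 that prevalent users are not included, and link the limitation in section 8.2 to the look-back.

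The cost is revised wording, one extra run of the objective 1 tables with a date filter, and two form items in charts that will be opened anyway. Section 6.5 limits access to patient identity to validation of the diagnoses, so that wording may need widening. The sample sizes of 173 and 122 can stay, because the full cohort is kept.

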6.1.2. Registry characteristics

The RPT is a register implemented in Catalonia by health professionals from the Comprehensive Public Health System of Catalonia (SIS CAT) to carry out the task of monitoring the data on the use of high-cost drugs in normal clinical practice conditions. All the hospitals named above participate in the RPT. The general structure of the registry consists of three levels of information: treatment level, initiation level and follow-up level. Treatment level includes basic patient data, the identification of the treatment and identification of the origin of the prescription. The initiation level includes the clinical variables that are required when initiating a treatment such as the

indication. Lastly, the follow-up level includes the clinical variables that are required during the treatment follow-up and the discontinuation variables at the end of the treatment (Roig Izquierdo, 2020). The RPT does not register any concomitant medications or comorbidities.

6.1.3. Participating centers

In this study three third-level hospitals will participate:

- **Hospital Vall d'Hebron (HUVH)** is the largest hospital complex in Catalonia and one of the largest in Spain. It is structured into three main health areas: General Area, Mother and Child Area and Orthopedics and Rehabilitation Area. With 1,146 beds, the hospital is committed to a management model that places patients at the center of its actions and promotes participation in Catalan and Spanish research projects.
- **Hospital Universitari de Bellvitge (HUB)** is a public hospital located in the town of l'Hospitalet de Llobregat. It is specialized in high complexity medical care and has 708 beds. It offers all the medical specialties, except for pediatrics and obstetrics. Bellvitge University Hospital, together with the University of Barcelona, the Catalan Institute of Oncology and the IDIBELL Research Institute, make up the Bellvitge Campus.
- **Hospital Universitari Germans Trias i Pujol (HGTiP)** is one of the large university hospitals (almost 650 beds) located at the foot of the Sierra de la Marina, in the municipality of Badalona. It provides direct healthcare to 250.000 citizens and is a referral center for high-tech care for 820.000 citizens in the surrounding areas. It also has an associated center devoted to research, the Health Sciences Research Institute Germans Trias i Pujol (IGTP).

To facilitate the collaboration between the hospitals, an operationalization tasks document was created to estimate workload and provide data sharing instructions (Annex 3)

6.2. Descriptive use methods (objective 1)

All patients starting a treatment with non-specific immunoglobulines (naive incident users) in the period between September 2019 and December 2021 regardless of their age, sex, indication, dose and duration of treatment.

6.2.1. Exposures

All the patients included in the study are exposed to non-specific immunoglobulines, this could be an extra- (J06BA02) or intravascular (J06BA01) administration.

List of definitions:

Naive incident user: a patient who isn't exposed to immunoglobulines (intra- or extravascular) a year prior to the start of the treatment with a non-specific immunoglobulin.

Immunoglobulin switching: the patients who changed immunoglobulin therapy from extravascular to an intravascular administration or vice versa during the study period providing that the period in between therapies is less than a year, regardless of the indication. In cases where two immunoglobulin types overlap in time, we won't consider them as switchers.

Immunoglobulin concomitance: if an overlapping use of an intravascular and an extravascular immunoglobulin of at least one day, regardless of indication. If cases are found they will be narratively described.

Immunoglobulin discontinuation: the patients who stopped the use of any type of non-specific immunoglobulines (J06BA01 and J06BA02) for a year or longer.

Duration of treatment: When there is a certain period between the start date and end date of the use of immunoglobulin.

Patients with multiple indications: In RPT each treatment initiation is linked to a single indication. When a patient meets multiple treatment initiations, different diagnosis for each may be found. In this case, if the patient does not meet any of the previous definitions (switching or discontinuation) and is treated with the same type of IGG administration (extra- or intravascular), they will be reviewed case by case. From this review, it will be decided based on medical criteria whether diagnoses are a specification of the other (e.g., transplant versus transplant rejection), or if they are clearly referring to different clinical entities. For both situations, if cases are found they will be narratively described.

These group of patients will not be taken into account during the validation of the RPT (see 6.3).

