6.3.1. Sample size calculation

For the sample size calculation for the validation of the indications in the RPT, the Granmo online calculator was used (https://www.imim.es/ofertadeserveis/en_granmo.html). It was determined that for a total of 500 RPT records, a random sample of 173 individuals was sufficient to estimate the validity of the register with a confidence interval of 95% and a precision of +/- 5%. The expected proportion was 78%, based on a similar previous study (R. Izquierdo et al 2020) and a replacement rate was not taken into account due to study validation design.

Of the 500 records, 224 belong to the Vall d'Hebron Hospital. This means that, with the same conditions as mentioned above, the sample size of the validation for the Vall d'Hebron Hospital will be 122. The number of validations is calculated in the same way for the other hospitals.

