6.3.2. Validation form

A validation form has been built using RedCap (RedCap, 2019). This standard validation form is user-friendly and should be used across multiple centers to ensure proper validation and uniformity of information. The form includes sex, year of birth, indication of RPT (including ICD10) and indication(s) of SAP (including ICD10). Finally, the reviewer can mark the matching status as correct, missing, incorrect and doubtful. If the **full** code in the RPT corresponds with the code in the clinical history the status could be classified as correct. Missing means that the reviewer has not enough information in either RPT or SAP to draw a conclusion. The reviewer can mark a case as incorrect when the two diagnoses are not equivalent or do not belong to the same ICD subgroup. When there is no code in the clinical history the diagnosis would be written down as free text, these cases will be reviewed case by case. In case of doubt, the reviewer can specify the doubt in the form. Doubtful cases will be discussed and a consensus will be reached within the research team. All cases will be reviewed by two different observers in order to map out the reliability of the validation [see *paragraph 6.3.3.*]. This form can be found in Annex 8.

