6.3.3.1. Positive predictive values

The positive predictive value is a measure used in the context of the evaluation of screening and diagnostic procedures, in addition to sensitivity and specificity [annex 9], the positive predictive value (PVV) is the proportion of patients truly diagnosed as positive to all those who had positive test results (Szklo, 2014). In this validation, the PVV is calculated by dividing the cases with diagnosis in RPT which are equivalent to the clinical history to all the cases of RPT indications ($A/(A+B)$), according to figure 1.

		CLINICAL HISTORY (CH)		
		YES	NO	TOTAL

RPT REGISTER	YES	A Diagnose in RPT equal* to CH (VP)	B Diagnose in RPT different than CH or absent	POSITIVES
	NO	C No Diagnose in RPT	D No Diagnose in RPT and no DX in CH	NEGATIVES
	TOTAL	DX in CH		

Figure 1: measures of validity of categorical data. Sensitivity: $A/(A+C)$; specificity $B/(B+D)$; positive predictive value: $A/(A+B)$; negative predictive value $D/(C+D)$.

[figure not shown]
*If the full code in the RPT corresponds with the code in the clinical history the status could be classified as correct. When there is no code in the clinical history the diagnosis would be written down as free text, these cases will be reviewed case by case.

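### Patients whose same-route RPT diagnoses differ are left out of the validation, so the PPV describes a selected subset and can be inflated

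*SAP*

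**What the plan says.** SAP section 6.2.1 starts from the structure of the register: "In RPT each treatment initiation is linked to a single indication". A patient with several initiations can therefore carry several diagnoses. The special group is formed "if the patient does not meet any of the previous definitions (switching or discontinuation) and is treated with the same type of IGG administration". For these patients "it will be decided based on medical criteria whether diagnoses are a specification of the other" or whether they refer to separate clinical entities. The outcome is a narrative: "For both situations, if cases are found they will be narratively described". The paragraph closes with the exclusion: "These group of patients will not be taken into account during the validation of the RPT (see 6.3".

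Section 6.3 does not carry this rule forward. Section 6.3.1 states that "for a total of 500 RPT records, a random sample of 173 individuals was sufficient", and 500 is also the approximate number of all eligible patients in section 6.1.1. Section 6.3.3.1 computes the PPV by "dividing the cases with diagnosis in RPT which are equivalent to the clinical history to all the cases of RPT indications". For the match itself, section 6.3.2 requires that the full "code in the RPT corresponds with the code in the clinical history the status could be classified as correct". The limitations in sections 8.1 and 8.2 do not mention the exclusion.

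**The concern.** Objective 2 is to validate the recorded indication. The exclusion is defined by that same variable: a patient leaves the validation because his or her own RPT indications disagree. The PPV then no longer estimates the accuracy of the register's indications. It estimates accuracy among patients without such disagreement, while 6.3.1 and 6.3.3.1 read as if it covered everyone.

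The two objectives also come apart. Section 6.2 keeps every naive incident user in the descriptive analysis whatever the indication, and section 8.1 justifies the validation by the RPT's importance for that objective. Part of the material used for objective 1 would lie outside the population to which the PPV applies. The case-by-case review does not close this gap. As described, it weighs the RPT diagnoses against each other rather than against the clinical history, and it yields no PPV.

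**Working it through.** **1. The plan's own sample sizes.** Inputs from 6.3.1: expected proportion p = 0.78, precision d = 0.05, 95% confidence, N = 500 overall and N = 224 for Vall d'Hebron.

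- n0 = 1.96² × 0.78 × 0.22 / 0.05² = 263.68
- n = n0 / (1 + (n0 − 1)/N)
- N = 500: 263.68 / (1 + 262.68/500) = 172.9, so 173
- N = 224: 263.68 / (1 + 262.68/224) = 121.4, so 122

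Both stated figures reproduce. Taking the group out of the frame changes the overall n very little: 172, 170, 167 and 160 for 2, 5, 10 and 20% removed (N = 490, 475, 450, 400). The issue is which population is sampled, not how many are drawn.

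**2. The bias.** Let f be the share of records excluded.

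- PPV(all) = (1 − f) × PPV(retained) + f × PPV(excluded)
- PPV(retained) − PPV(all) = f × (PPV(retained) − PPV(excluded))

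The SAP gives neither f nor the excluded PPV, so the values below are assumptions. The retained PPV is set at the SAP's expected 78%.

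| f | Overstatement, excluded PPV 60% | Overstatement, excluded PPV 30% |
|---|---|---|
| 2% | 0.02 × 0.18 = 0.4 points | 0.02 × 0.48 = 1.0 points |
| 5% | 0.9 | 2.4 |
| 10% | 1.8 | 4.8 |
| 20% | 3.6 | 9.6 |

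If the excluded records match 78% of the time, the bias is zero. If they match 90% of the time, it is negative: at f = 10%, 0.10 × (0.78 − 0.90) = −1.2 points.

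**3. When the bias reaches the planned ±5 points.** f = 0.05 / (0.78 − PPV(excluded)), which gives 10.4% at an excluded PPV of 30%, 13.2% at 40%, 17.9% at 50% and 27.8% at 60%.

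**4. Why upward is the likelier direction.** A record counts as correct on a full-code match. If the clinical history supports a single full code for the course of treatment, two initiations with different RPT codes cannot both match, so at most one of the two is correct. The SAP's example of one diagnosis specifying another (transplant and transplant rejection) can be of this kind. The argument fails where the history supports both codes.

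**The case against.** A reader might infer that the excluded records are the ones most likely to be wrong and that the PPV is certainly biased upwards. The SAP does not support that. Section 6.2.1 foresees two outcomes of the review, a specification or a different clinical entity, and neither is a coding error. A patient may have two true indications, and the form in 6.3.2 allows more than one indication from the clinical history. That section also reserves the incorrect status for diagnoses that are not equivalent or fall in different ICD subgroups, so a less specific code need not be counted as wrong. This part of the objection stands: the direction is an inference.

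Nor are all patients with several differing indications removed. The rule covers only those on one route who meet neither the switching nor the discontinuation definition, so the exclusion does not reach switchers and discontinuers.

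The group may also be small. The SAP speaks only of cases being found, and f = 20% would mean about 100 of 500 patients. At f of 2 to 10% the computed shift stays below the planned precision. That stands too, but a shift inside the interval is not harmless. A half-width of 5 points implies a standard error of 5/1.96 = 2.55 points, and a bias of that size lowers the coverage of a nominal 95% interval to about 83%. A larger sample would not remove it.

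Finally, the group is reviewed and described, not silently dropped, and most patients outside the sample of 173 also enter objective 1 unchecked. But an unsampled patient is represented by the random sample, and an excluded patient is not.

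**Conclusion.** The exclusion is real and unexplained, depends on the variable being validated, and is inconsistent with the PPV denominator in 6.3.3.1 and the frame in 6.3.1. Followed as written, the plan yields a PPV for a selected subset and presents it as the register's.

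The PPV can be inflated, more likely than deflated under the full-code rule. With a retained PPV of 78%, an excluded share of 2 to 10% and an excluded PPV of 30 to 60%, all assumed, the overstatement is about 0.4 to 4.8 points. It vanishes if the excluded records match as often as the others. A claim that it exceeds the planned ±5 points would need an excluded share above roughly 10 to 28%, depending on the excluded PPV, and nothing in the SAP indicates a share that large.

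**What to change.** Delete the exclusion sentence in 6.2.1 and keep these patients in the sampling frame. For each sampled patient, compare the code or codes recorded at initiation level with the clinical history for that initiation. Report how many such patients there are, and the PPV with and without them. If more than one record per patient enters the analysis, use a patient-clustered standard error. Section 6.3.1 should also say whether the frame and sample count records or individuals, since it currently uses both terms.

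The cost is modest: some date-specific matching during chart review, a revised frame count, and sample sizes recomputed from it with the same formula. The number of charts need change little, if at all.

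If the exclusion is kept, give its reason and the number excluded, state in 6.3 that the PPV applies only to the remaining patients, and add this to the limitations in section 8.
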